The Evaluation Of The Efficiency Of Micro- osteoperforation

Date :April 28, 2016

STUDY PROTOCOL

The aim of this study was to evaluate the effectiveness of micro-osteoperforations (MOP) performed in the alignment stage.

This was a 2-arm parallel-group, randomized, controlled trial with a 1:1 allocation ratio

The protocol of the study was approved by Izmir Katip Çelebi University Clinical Research Ethics Committee dated 18.05.2016 (no: 94) and T.C. Ministry of Health, Turkey Pharmaceuticals and Medical Devices Agency dated 09.09.2016 (document number: 228 418) was approved by decision.

Based on Mehr's (1) study, the dependent sample t-test using the G * Power 3.1 software program (Franz Faul, Universität Kiel, Germany) showed that 24 patients had an effect width of $d = 1.05$ and $\alpha = 0.05$ significance level. it was determined that the number of samples formed 80% power. Assuming a 15% exclusion rate, a total of 28 patients (14 patients) were included in the study.

The patients who applied to the Department of Orthodontics of the Faculty of Dentistry of Izmir Katip Çelebi University and who were found to comply with the study criteria were informed verbally and in writing. Written informed consent was obtained from patients and parents who agreed to participate in the study. A total of 28 patients (12 males and 16 females) aged between 12 and 27 years, with a diameter of more than 5 mm in terms of the Little irregularity index, were included in the study. The study groups were composed of 14 patients (4 boys, 10 girls) in the MOP applied (MOP+) group and 14 patients (8 boys, 6 girls) in the MOP not applied (MOP-) group.

The following inclusion and exclusion criteria were considered in the selection of patients to be treated: Inclusion Criteria:

- All permanent teeth have been removed (except the 3rd molars)
- Presence of more than 5 mm crowding in the lower arc according to Little irregularity index (1)

- Gingival and periodontal indices less than 1
- Good oral hygiene
- Patient and / or guardian volunteering to participate in the study
- Exclusion Criteria:
 - Congenital missing or pulled teeth
 - Severe skeletal malocclusion
 - Systemic disease
 - Presence of periodontal disease
 - Radiographic determination of bone loss

- Gingival pocket depth of more than 4 mm • Previous orthodontic treatment

Table 1 presents the gender, age distribution and baseline Little irregularity index data of the patients. Table 1: Gender distribution by groups, mean age and perceptions.

GROUPS	MOP+		MOP-		TOPLAM		p
	n	%	n	%	n	%	

Female	10	71,46	42,9	16	57,10		
Male	4	28,68	57,1	12	42,90		
total	14	100	14	100	28	100	
	\bar{x}	ss	\bar{x}	ss	\bar{x}	ss	p
Little irregularity index	9,99	2,63	8,87	1,50	9,42	2,17	0,179
age (years)	17,21	3,76	15,29	1,77	16,25	3,05	0,095

n: number of individuals \bar{x} : average, ss: standard deviation, p<0,05

Oral hygiene procedures were explained visually with videos and applied on the model to all patients before the treatment and in the session where the brackets were applied. It was told that they should brush their teeth at least 3 times a day, then use an interface brush, pay attention to the foods that will cause caries and avoid acidic beverages. Periodontal status of the individuals included in the study before the treatment was evaluated with the help of periodontal measurements. Oral hygiene of the individuals included in the study was checked at each session and necessary suggestions were made.

The pre-treatment routine orthodontic recordings of the individuals included in the study were performed by taking plaster model, intraoral and extraoral photographs, panoramic and lateral cephalometric radiographs and evaluations according to inclusion criteria.

In each study, clinical periodontal parameters were measured with periodontal sonde just before (T0) and after the leveling (T1) treatment. Gingival thickness measurements were performed with an

ultrasonic device (Pirop® Ultrasonic Biometer A- Scan, Echo - Son, Krancowa, Poland).

In order to evaluate the changes in the dental arch until the leveling phase was completed, each session was taken from the lower jaw and plaster models were obtained. Afterwards, digital models were created from plaster models using 3D scanning device (3Shape R700 TM Scanner, Copenhagen, Denmark).

In our study, bracketing was performed by using MBT system brackets (Mini Master Series® 2, American Orthodontics, Sheboygan, WI, USA) with 0.022x0.028 inch slots in both groups. After bracketing and before MOP administration, patients were asked to rinse their mouth twice with chlorhexidine mouthwash, each lasting for 1 minute. In the first session, MOP application was performed with Propel® (Ossining, NY, USA) driver under local anesthesia in the areas where the dental movement was requested in accordance with the manufacturer's instructions.

Propel® is a disposable device specially designed for micro-osteoperforation. The device includes a 1.5 mm thick perforation tip. It has a depth setting of 3, 5 and 7 mm and the LED depth indicator warns when the desired depth is reached. The device was removed from its sterile packaging and, after adjusting the desired depth, was gently placed on the gum and then turned clockwise with gentle pressure. When the desired skin was reached, the LED indicator was removed by turning it counterclockwise with the indicator illuminated. Micro-osteoperforations were performed directly and atraumatically in the keratinized gum at two or three points, 3 mm between canine canine, 5 mm between canine molar, and 7 mm deep in the posterior region and 1.5 mm in diameter in the alveolar bone (2).

In each group of patients using conventional fixed orthodontic braces, leveling with 0.014 inch nickel titanium (Ni-Ti, American Orthodontics, Sheboygan, WI, USA) arc wire was started. All patients were called for monthly visits and each session was measured and a plaster model was formed until the leveling phase was completed. Ni-Ti (American Orthodontics, Sheboygan, WI, USA) wires of 0.014 inch, 0.016 inch, 0.016x0.022 inch and finally 0.019x0.025 inch were used, respectively, depending on the leveling condition. In both groups, arc wires were connected to the slots by prefabricated steel wire ligatures.

In order to evaluate the clinical efficacy of micro-osteoperforation, the following variables were evaluated in both groups at the beginning of treatment and after completion of the leveling:

- Cephalometric measurements
- Periodontal measurements
- Amount of entanglement and width of tooth arch
- Leveling time
- Pain values and patient satisfaction

Evaluation of Hard and Soft Tissue Changes

Angular and linear measurements were performed on lateral cephalometric films taken at the beginning and after treatment.

Lateral Cephalometric Radiography

The lateral cephalometric radiographs used in the study were taken with cephalometric x-ray device (Orthopantomograph, OP300, Scanora / Instrumentarium, Tuusula, Finland) in the Department of Oral

Diagnosis and Radiology of Izmir Katip Celebi University Faculty of Dentistry. Lateral cephalometric radiographs; natural head position, teeth in centric occlusion and lips in resting position. In order to perform cephalometric analysis, 24 points were determined and 9 cephalometric planes were created. A total of 13 measurements were performed using 4 skeletal, 6 dental and 3 soft tissues using Dolphin Imaging software (version 11.8, Dolphin Imaging, Chatsworth, CA, USA).

Cephalometric Points Evaluated in the Study

The points to be used for cephalometric analysis were grouped into 3 groups as skeletal, dental and soft tissue points.

Evaluation of Periodontal Tissues

Gingival index (GI), plaque index (PI), pocket depth (PD), probing bleeding (PB) and gingival thickness (GT) were measured when immediately before placing the bracket (T0) and after completion of the leveling procedure (T1) in all patients in the study. Periodontal measurements were performed by a single researcher in order to provide standardization. Probing was performed using the Williams periodontal probe (Hu Friedy®, Chicago, IL, USA) with a diameter of 0.5 mm and a guide line at 1-2-3- 5-7-8-9-10 mm on it to facilitate measurement. The measurements were recorded in clinical forms of each patient.

The gum thickness was measured using an ultrasonic measuring device (Pirop® Ultrasonic Biometer, A- Scan, Echo - Son, Krancowa, Poland) at the midline of the tooth, perpendicular to the tooth, in the middle of the keratinized gingival width (3).

Properties of Pirop® Biometer:

1. The device measures from 0.25 to 6 mm.
2. It shows sensitivity up to 0.01 mm.
3. It has an A-scan tip at a frequency of 20 MHz (4).

4. It transmits 10 ultrasonic waves to the application area and works on the principle of giving 10 gum thickness measurements by automatically calculating the distance traveled in mm as a result of the reflection of the ultrasonic waves from the hard tissue.

5. Automatically subtracts the average value from 10 measurements and reflects the results to the 5.7- inch LCD touch screen with standard deviation.

With a 45 degree angle between the holding portion and the tip device, the conical tip 1.7 mm in diameter perpendicular to the teeth, without stressing the soft tissue, the measurement was carried out by applying to the mucosal outer surface. If the standard deviation of the 10 automatic mean values exceeds 0.05 mm, the gum thickness measurement was repeated.

Evaluation of Digital Model

In our study, nickel titanium (Ni-Ti, American Orthodontics, Sheboygan, WI, USA) wires were applied to the patients in appointments according to the current situation. Each session is used to record the current situation until the session in which 0.019x0.25 inch Ni-Ti wire is attached; T0 (start, n = 28), T1 (second session, n = 28), T2 (third session, n = 28), T3 (fourth session, n = 28), T4 (fifth session, n = 28), T5 (sixth session, n (MOP +) = 7, n (MOP -) = 9) plaster model was obtained from patients. In both groups, a smaller number of models were obtained in the T5, since some of the patients had previously inserted 0.019x0.25 inch Ni-Ti wire.

Plaster models were converted to digital models using a scanning device (3Shape R700 TM Scanner, Copenhagen, Denmark). Dental models were performed on digital models with the software program (OrthoAnalyzer TM, Copenhagen, Denmark).

In order to analyze changes in dental arches; Intermolar distance, intercanine distance, arc length, arc depth and Little perpendicularity index measurements were made in horizontal plane.

Points Used in Model Analysis

- 1) L6F (right and left): Central fossas of the lower molar teeth
- 2) L3T (right and left): Tuberule tips of the lower canine teeth
- 3) L6MCP (right and left): Mesial contact points of the lower molar teeth
- 4) L1-1CP: The intersection of the contact points of the lower central incisors
- 5) L1MCP, L2MCP, L3MCP: Lower central, lateral and canine tooth mesial contact points
- 6) L1DCP, L2DCP: Distal anatomical points of the lower central and lateral teeth

Measurements in Model Analysis

- 1) Intermolar distance: Distance between right and left L6F
- 2) Intercanine distance: Distance between right and left L3T
- 3) Lower arc length: Sum of the distance between the contact points of the lower incisors (L1-1CP) and the mesial contact points (L6MCP) of the right and left lower molars

4) Lower arc depth: The distance between the intersection of the contact points of the lower incisors (L1-1CP) and the line connecting the mesial contact points (L6MCP) of the right and left lower molars.

5) Little irregularity index: Measure the distance between the teeth in the mandibular anterior region from the canine tooth's mesial (L3MCP) to the canine's mesial (L3MCP) on the other side with its own anatomical contact points (L1MCP, L2MCP, L1DCP, L2DCP) in the horizontal plane and add five measured values obtained (5).

Evaluation of Leveling Times

In assessing the leveling time in the lower jaw, the Little irregularity index was considered (5). The time from the beginning of treatment (T0) until the leveling was completed (T1: Little irregularity index falling below 1 mm) was calculated in days (6).

Evaluation of Pain and Patient Satisfaction During Treatment

A questionnaire was performed to assess pain and patient satisfaction at the beginning of treatment (T0), 1 hour later (T1), 12 hours later (T2), 7 (T3), 14 (T4) and 28 (T5) days (5). Visual analog scale (VAS) method was used for pain scoring, there is a range of 0–10, “no pain - unbearable pain” symbolizes information.

References

1. Mehr R. Efficiency of piezotome-corticision assisted orthodontics in alleviating mandibular anterior crowding—a randomized controlled clinical trial. 2013.
2. Propel orthodontics products-Treatment guide <https://www.propelorthodontics.com/wp-content/uploads/2015/01/Treatment-Guide.pdf> [
3. Bednarz W. The thickness of periodontal soft tissue ultrasonic examination—current possibilities and perspectives. *Dental and Medical Problems*. 2011;48(3):303-10.
5. Little RM. The irregularity index: a quantitative score of mandibular anterior alignment. *American journal of orthodontics*. 1975;68(5):554-63.

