The Evaluation Of The Efficiency Of Micro-osteoperforation

Date :April 28, 2016

Statistical Analysis Plan (SAP)

Data were analyzed by IBM SPSS (version: 25.0, IBM Corp., Armonk, New York, USA) statistical package program. Descriptive statistical data were number of units (n), percentage (%), mean \pm standard deviation ($\bar{x} \pm$).

Correlation between the measurements (method error) was evaluated with intraclass correlation coefficient. In the assessment of the compatibility of the Model and Little perpendicularity index measurements, the intraclass correlation coefficient was specified with a 95% confidence interval.

The normal distribution of the numerical variables was evaluated by Shapiro-Wilks normality test and Q-Q graphs. Independent samples t test was used to compare the means between two independent groups of continuous measurements, and dependent sample t test was used to compare two dependent groups. Gender distribution between groups was evaluated using chi-square test.

The comparison of the groups according to time was made by means of two-way analysis of variance and generalized linear models in repeated measurements. Bonferroni test was used as multiple comparison test. The level of statistical significance was set at $p \leq 0.05$.

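### The sample-size paragraph names a paired t-test for a two-arm parallel trial; 24 patients follows only from an undeclared one-sided independent test, and two-sided power is 69.1% at 24 and 76.2% at 28

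*Protocol*

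**What the plan says.** The protocol's opening section gives the design: "This was a 2-arm parallel-group, randomized, controlled trial with a 1:1 allocation ratio". Its sample-size paragraph takes an effect size of d = 1.05 from an earlier trial and an alpha of 0.05. It cites "the dependent sample t-test using the G * Power 3.1 software program" and says of 24 patients that "it was determined that the number of samples formed 80% power". A 15% exclusion allowance then raises the number to 28, or 14 per arm. The paragraph does not name the outcome to which d = 1.05 belongs, and does not say whether the test is one- or two-sided.

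The SAP separates the two t-tests. For independent groups: "Independent samples t test was used to compare the means between two independent groups of continuous measurements". For paired data: "dependent sample t test was used to compare two dependent groups". On significance it gives only a threshold ("The level of statistical significance was set at" p ≤ 0.05), again without sidedness. It also lists repeated-measures analyses for comparing the groups over time.

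**The concern.** A dependent-sample t-test is for paired measurements. Here each patient belongs to one arm, so the between-arm comparison has no pairs. The named test therefore conflicts with the design and with the SAP. The choice also changes the answer, because at the same d and alpha a paired test needs far fewer subjects than an independent one. If the stated inputs do not lead to 24, the reader cannot tell which calculation was done or which power applies. That matters most if the result is not significant, when the reader needs to know how likely the trial was to miss a true effect of the planned size.

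**Working it through.** **Inputs.** d = 1.05, alpha = 0.05, target power 80%, 24 patients before exclusions and 28 after (protocol, sample-size paragraph); two arms, 1:1 (protocol, design statement). Sidedness is not stated, so both cases are computed.

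**Formulas (exact noncentral t).**
- Paired, n pairs: df = n − 1, noncentrality d√n.
- Independent, n per arm: df = 2n − 2, noncentrality d√(n/2).
- One-sided power = P(T > t at 1 − 0.05). Two-sided power = P(|T| > t at 1 − 0.025).

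**Step 1: reproduce 24 with the named test.**
- Two-sided: 9 pairs give 78.7% and 10 pairs give 83.9% (noncentrality 1.05 × √10 = 3.32), so 10 are needed.
- One-sided: 7 pairs give 78.9% and 8 pairs give 84.7%, so 8 are needed.
- With 24 pairs the noncentrality is 1.05 × √24 = 5.14 and two-sided power is 99.8%. For 24 pairs to give 80% two-sided, d would have to be about 0.60.

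The named test does not give 24.

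**Step 2: try the independent test.** Noncentrality is 1.05 × √6 = 2.57 at 12 per arm and 1.05 × √7 = 2.78 at 14 per arm.

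| Per arm (total) | One-sided 0.05 | Two-sided 0.05 |
|---|---|---|
| 11 (22) | 76.8% | 64.9% |
| 12 (24) | **80.1%** | 69.1% |
| 14 (28) | 85.5% | **76.2%** |
| 15 (30) | 87.7% | 79.3% |
| 16 (32) | 89.6% | 82.0% |

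One-sided, 12 per arm is the smallest size that reaches 80%, so the stated 24 is reproduced exactly. Two-sided, the smallest is 16 per arm, or 32 evaluable. Simulation of 400,000 trials agrees: two-sided 69.2% and 76.3%, one-sided 80.2% and 85.6%, at 12 and 14 per arm.

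**Step 3: size of the two-sided gap.**
- With 28 patients the chance of missing d = 1.05 is 100 − 76.2 = 23.8%, against a planned 20%.
- With 24 it is 100 − 69.1 = 30.9%.
- The effect detectable with 80% power is d = 1.10 at 28 and d = 1.20 at 24.
- If 1.05 is a rounded value (1.045 to 1.055), two-sided power ranges over 75.9–76.6% at 28 and 68.7–69.5% at 24, and 16 per arm is still needed.

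**Step 4: what the documents show about sidedness.** Table 1 gives baseline p-values of 0.179 (Little irregularity index) and 0.095 (age). Pooled t-tests from the printed means and standard deviations, 14 per arm:
- Index: difference 9.99 − 8.87 = 1.12; pooled SD √[(2.63² + 1.50²)/2] = 2.14; standard error 2.14 × √(2/14) = 0.81; t = 1.38; two-sided p = 0.178.
- Age: difference 17.21 − 15.29 = 1.92; pooled SD √[(3.76² + 1.77²)/2] = 2.94; standard error 1.11; t = 1.73; two-sided p = 0.096.

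Both match two-sided tests within rounding. This is indirect evidence only, because these are baseline comparisons and not the efficacy test.

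**The case against.** The strongest reply is that this is one wrong word in loosely translated text. The SAP makes clear that the arms are compared with an independent test, and 24 is an exact answer for that test done one-sided, so the arithmetic behind 24 may be sound. That much stands: the number itself is not shown to be wrong. But the match also requires one-sided testing, which neither document declares, so correcting the word does not settle the power.

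A second reply is that the protocol attaches 80% to 24 patients and never claims it for 28. That is right. The like-for-like two-sided contrast is 69.1% against 80%, which is the larger gap. The figure at 28 shows that even full retention does not reach 80%.

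A third is that the model counts ("T3 (fourth session, n = 28), T4 (fifth session, n = 28") do not fix the evaluable number for leveling time, pain or the periodontal outcomes. This also stands, since d = 1.05 is tied to no outcome. The section on digital models does report 28 models at each of T0 to T4, and attributes the smaller T5 counts to patients who already had the final wire. For model outcomes 28 is therefore the better guide; for others, both sizes should be given.

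Finally, a normal approximation gives 79.3% at 28 two-sided, close to 80%. The protocol cites a t-test in G*Power, and with 14 per arm the exact t calculation is the appropriate one. The approximation also falls short, and gives only 73.0% at 24.

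**Conclusion.** The concern holds. Two parts are unconditional: the named test does not fit the design, and with the stated inputs it gives 8 or 10 patients, not 24. The power shortfall is conditional on sidedness. Two-sided at 0.05, the 80% claim becomes 69.1% at 24 evaluable and 76.2% at 28; one-sided at 0.05, it is met. The Table 1 p-values lean towards two-sided practice without proving it for efficacy.

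The figures assume d = 1.05 as stated, equal arms, and a single between-arm comparison of means by t-test. They do not apply to the repeated-measures analyses in the SAP. The gap at 28 is modest (3.8 percentage points), so this should be corrected but does not undermine the trial.

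**What to change.** In the protocol's sample-size paragraph:
- Replace the dependent test with the independent-samples t-test, checking the saved G*Power inputs if they still exist.
- Name the outcome to which d = 1.05 refers.
- State whether the between-arm test is one- or two-sided, and say the same in the SAP beside the significance level.

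Then state the matching power:
- If two-sided: about 76% with 28 patients (detectable d 1.10), and 69% in the planning case of 24 evaluable (detectable d 1.20), in place of 80%.
- If a one-sided 0.05 test was in fact prespecified: say so in both documents, with 80.1% at 24 and 85.5% at 28.

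Both documents describe the 28 patients as already included, so no change in sample size is asked for. The cost is one corrected paragraph in the protocol and one sentence in the SAP. If testing is two-sided, the stated power becomes less favourable.

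### Change in the Little index from T0 to completion of leveling mostly restates the baseline difference, and the SAP does not say that crowding efficacy is instead judged at the fixed sessions T1 to T4, adjusted for T0

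*Protocol*

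**What the plan says.** The protocol's list of efficacy variables, just before the heading Evaluation of Hard and Soft Tissue Changes, states that "the following variables were evaluated in both groups at the beginning of treatment and after completion of the leveling". One of its five entries is "Amount of entanglement and width of tooth arch", which covers crowding and arch width. Leveling time is a separate entry.

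Evaluation of Leveling Times defines leveling time as "The time from the beginning of treatment (T0) until the leveling was completed" and marks the end as "T1: Little irregularity index falling below 1 mm". The same index is the protocol's measure of crowding. Patients enter on "Presence of more than 5 mm crowding in the lower arc according to Little irregularity index".

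Evaluation of Digital Model sets a different end for the model series: "Each session is used to record the current situation until the session in which 0.019x0.25 inch Ni-Ti wire is attached". It reports models for all 28 patients at T0 to T4, and for 7 MOP+ and 9 MOP- patients at T5. Visits are monthly.

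The SAP names an independent-samples t test for two groups, and says that "dependent sample t test was used to compare two dependent groups". It also names repeated-measures two-way analysis of variance and generalized linear models for comparing the groups over time, with Bonferroni correction. It attaches none of these to a named outcome and mentions no adjustment for baseline.

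**The concern.** If efficacy on crowding is read at completion, and completion means that crowding has reached a set value, the outcome is measured at the moment it is required to be nearly the same in everyone. A treatment that speeds alignment changes when a patient gets there, and hardly changes where the patient ends. The change from T0 to that point then reflects mainly how crowded the patient was at the start.

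MOP+ started more crowded on average, so this comparison would show a larger correction in MOP+ with no treatment effect at all. A paired test within each arm would look like strong evidence, although the entry and completion rules between them produce it. A reader of the trial report could take either result as evidence for MOP.

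**Working it through.** **Inputs.** From Table 1, the baseline Little index (mean, SD) is 9.99, 2.63 in MOP+ and 8.87, 1.50 in MOP-, with n = 14 per arm and a stated p of 0.179. The entry rule is an index above 5 mm. The completion rule is an index below 1 mm.

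**1. Reproduce the plan's baseline figure.**
- Difference = 9.99 - 8.87 = 1.12 mm.
- SE = sqrt((2.63² + 1.50²)/14) = sqrt(9.167/14) = 0.809.
- t = 1.12/0.809 = 1.38 on 26 df, p = 0.178 (0.181 by Welch). This agrees with the stated 0.179.
- 95% CI = 1.12 ± 2.056 × 0.809 = -0.54 to 2.78 mm. The p-value therefore does not show that the arms are balanced.

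**2. Bounds on the change, with no distributional assumption.** If every patient completes with an end value between 0 and 1 mm, change = baseline - end value.
- MOP+ mean change lies between 9.99 - 1 = 8.99 and 9.99 mm.
- MOP- mean change lies between 8.87 - 1 = 7.87 and 8.87 mm.
- The difference in mean change lies between 8.99 - 8.87 = 0.12 and 9.99 - 7.87 = 2.12 mm. This is the baseline difference plus or minus at most 1 mm, and it is positive throughout.

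**3. Within-arm paired test.** The SD of 14 values confined to 0-1 mm is at most 0.5 × sqrt(14/13) = 0.52. The SD of the change is therefore at most 2.63 + 0.52 = 3.15 in MOP+ and 1.50 + 0.52 = 2.02 in MOP-.
- MOP+: t is at least 8.99/(3.15/sqrt(14)) = 10.7.
- MOP-: t is at least 7.87/(2.02/sqrt(14)) = 14.6.

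Both are on 13 df and far beyond any usual critical value.

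**4. Between-arm test if end values do not differ by arm.** Assume that end values are uniform on 0-1 mm in both arms (variance 1/12 = 0.083). The documents do not give this distribution.
- t = 1.12/sqrt((2.63² + 0.083 + 1.50² + 0.083)/14) = 1.12/0.816 = 1.37, p about 0.18. This is essentially the baseline test again.
- Share of the variance of change due to baseline: 6.917/7.000 = 99% in MOP+ and 2.250/2.333 = 96% in MOP-.
- In 100,000 simulated trials under this assumption, the mean difference in change was 1.12 mm and its correlation with the baseline difference was 0.99.

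**5. What fixed sessions can show (illustration).** Assume that both arms start at (9.99 + 8.87)/2 = 9.43 mm, that the index declines exponentially, that control reaches 1 mm at 5 months, and that MOP acts 1.5 times as fast. Then k = ln(9.43)/5 = 0.449 per month. At month 1, control is 9.43 × exp(-0.449) = 6.02 mm and MOP is 9.43 × exp(-0.673) = 4.81 mm, a difference of 1.2 mm. At months 2, 3 and 4 the differences are about 1.4, 1.2 and 0.9 mm. Over control times of 4 to 6 months and speed ratios of 1.25 to 2, the differences range from about 0.4 to 2.4 mm. If each arm is read when it reaches 1 mm, the difference is about 0 at every speed ratio.

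**The case against.** The strongest reply is that nobody planned the comparison criticised here. The lead-in to the efficacy list is loose and cannot be literal for every entry: leveling time has no value at the start, and pain has its own schedule out to 28 days. It says that variables were evaluated and names no change score or test. The index is measured at monthly sessions, with all 28 patients through T4, and the SAP's group-by-time analysis is a natural fit for those data. The t tests may be meant for the periodontal and cephalometric measures, which have only two time points. The below-1-mm rule appears only in the leveling-time section, whereas the model series ends at insertion of the final wire, where no bound on the index is stated. Finally, p of about 0.18 would not produce a significant between-arm result.

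Most of this stands, and it rules out a stronger reading. A reader might infer that the trial's crowding data cannot show a MOP effect, or that the two-point contrast is the only crowding analysis. The documents do not support either: the session data and the group-by-time analysis exist, and leveling time addresses speed directly. Nor does the argument reach arch width, which the completion rule does not constrain.

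The reply does not remove the gap. The lead-in is the only text that gives time points for crowding as an efficacy variable, and nothing in the SAP says that the session analysis takes its place. Ending at the final wire lifts the strict 1 mm bound, but wires were changed according to the state of leveling, so that reading is still triggered by response. A non-significant p does not make the contrast informative, because its estimate still leans towards MOP+.

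**Conclusion.** The point holds for the Little index from T0 to completion, with completion defined as an index below 1 mm. The arm difference in change is 1.12 mm plus or minus at most 1 mm. It favours MOP+ with or without an effect and carries almost no information on speed of alignment. It is not strictly empty, since a residual difference in end values of under 1 mm remains possible.

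The bounds rest on Table 1 and on all patients completing under that rule. The p of about 0.18 and the 96-99% shares also rest on the assumed uniform end values. The 0.4 to 2.4 mm range is an illustration and not a forecast.

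The trial's answer on MOP is not lost, because valid measures are already in the plan. What is missing is a statement of which crowding analysis carries the efficacy conclusion, and adjustment for the T0 index.

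**What to change.** - In the efficacy list and the SAP, state that the Little index at completion, and its change from T0 to completion, are descriptive only and are not evidence of efficacy.
- In the SAP, name the crowding efficacy analysis: the between-arm difference in the Little index at T1 to T4, from a repeated-measures model with arm, session and their interaction, adjusted for the T0 index. Report differences with 95% confidence intervals and the Bonferroni correction already named.
- Do not use T5 as a complete-case contrast. Its 7 and 9 patients are those who had not yet received the final wire, a subset selected by response.
- Leave speed of alignment to the leveling-time endpoint.
- Reconcile the two ends of leveling (insertion of the final wire in Evaluation of Digital Model, index below 1 mm in Evaluation of Leveling Times). Give T1 one meaning for the crowding data: it is the second session in the former section and completion in the latter.
- Label the change as made after data collection, because the documents already report baseline data and session counts.

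The cost is a few sentences and one model run. The session models exist for all 28 patients, so no new data are needed.

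### No masking is described for the person measuring the digital models, although arm is evident and leveling time depends on a 1 mm cut; coding the scan files would close this route for reading bias at small cost

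*Protocol*

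**What the plan says.** The opening of the protocol gives the design: "This was a 2-arm parallel-group, randomized, controlled trial with a 1:1 allocation ratio". The comparison is perforation against no perforation. The perforations are made under local anesthesia at the first session, and no sham is described for the other arm.

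Under Evaluation of Digital Model, plaster models from each session are scanned, and the index is measured on the scans: "Dental models were performed on digital models with the software program". The index is the sum of five distances between contact points of the lower anterior teeth. Evaluation of Leveling Times counts days from the start of treatment to completion, defined as "T1: Little irregularity index falling below 1 mm". (T1 here means completion; in the model section T1 is the second session.) Visits are monthly. The model series ends at the session when the last wire is attached.

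Two measurement safeguards are named. For the periodontal indices only, "Periodontal measurements were performed by a single researcher in order to provide standardization". For the models and the Little index, the second paragraph of the SAP plans an intraclass correlation with a 95% confidence interval. Neither document mentions blinding, masking, coding of files or reading order, or says who measured the models.

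**The concern.** The treating clinician and the patient necessarily know the arm. If the person placing the points on the scans also knows it, expectation can enter the reading. With a fixed cut and monthly models, a borderline reading decides which visit counts as completion, so a small systematic difference between arms becomes a difference in leveling time.

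The named safeguards do not address this. A single examiner removes variation between examiners but not that examiner's expectation. An intraclass correlation shows whether repeat readings agree; a reader who consistently reads one arm low can still agree very well with themselves. With 14 patients per arm, a few readings carry weight. At stake is a false or inflated difference in leveling time, one of the trial's key efficacy outcomes.

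**Working it through.** The plan gives no figure for reading bias, so there is none to reproduce. The question is how far an assumed bias would move leveling time.

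**Inputs from the documents.** Baseline index 9.42 mm (SD 2.17) overall, from Table 1; threshold 1 mm; monthly visits; 14 per arm; independent-samples t test at 0.05. All 28 patients have a fifth-session model and 7 + 9 = 16 have a sixth, so the series runs to roughly 4 or 5 months.

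**Assumptions.** One arm is read low by a constant b = 0.1, 0.2 or 0.3 mm. As the index sums five distances, 0.2 mm is 0.2/5 = 0.04 mm per distance. The time T to reach 1 mm is 4 to 6 months (121.6 to 182.4 days at 30.4 days a month), with 90 to 150 days as a shorter alternative. Decline is exponential or linear.

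**Shift in the crossing.** A reading b too low falls below 1 mm when the true index is 1 + b.

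- Exponential: shift = T × ln(1 + b) / ln(9.42), with ln(9.42) = 2.243. Example: 121.6 × 0.0953 / 2.243 = 5.2 days.
- Linear: shift = T × b / (9.42 − 1). Example: 121.6 × 0.1 / 8.42 = 1.4 days.

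| Bias | Exponential, 4–6 months | Linear, 4–6 months | Exponential, 90–150 days | Linear, 90–150 days |
|---|---|---|---|---|
| 0.1 mm | 5.2–7.8 days | 1.4–2.2 | 3.8–6.4 | 1.1–1.8 |
| 0.2 mm | 9.9–14.8 | 2.9–4.3 | 7.3–12.2 | 2.1–3.6 |
| 0.3 mm | 14.2–21.3 | 4.3–6.5 | 10.5–17.5 | 3.2–5.3 |

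**False-positive rate.** Two simulations used monthly readings, 14 per arm, no true effect and a two-sided t test.

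- Simulation A: baseline normal (9.42, 2.17) truncated at 5 mm, log-normal decline rate with SD 0.2, random reading error SD 0.1 mm, median crossing near 4.5 months.
- Simulation B: true time to 1 mm with mean 130 and SD 30 days, random reading error SD 0.2 mm, 4,000 trials per setting.

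| Setting | No bias | 0.1 mm | 0.2 mm | 0.3 mm |
|---|---|---|---|---|
| A, exponential | 5.2% | 7.0% | 14.4% | 26.0% |
| A, exponential, rate SD 0.4 | – | 6% | 8% | 11% |
| A, linear | – | 5.0% | 5.3% | 6.0% |
| B, exponential | 5.2% | 7.6% | 14.6% | 24.2% |
| B, linear | 4.8% | 5.6% | 6.0% | 6.4% |

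The Monte Carlo standard error at 5% with 4,000 trials is √(0.05 × 0.95 / 4,000) = 0.3 percentage points, so the linear rows are close to nominal.

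**Weight of single readings.** One borderline model read the other way moves that patient by about 30 days and the arm mean by 30/14 = 2.1 days. The arms differ by two patients in sixth-session models (7 against 9). If each stands for one extra month, that is 2 × 30/14 = 4.3 days.

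**Re-reading.** Suppose the series stops at the visit first read below 1 mm. Under simulation A with exponential decline, a fresh masked reading of that last model is 1 mm or more in about 12% of patients with no bias, and in about 38% of the favored arm when the first reading was biased by 0.2 mm. Masked re-reading therefore leaves some patients with no observed crossing.

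**The case against.** The strongest reply is that the documents are silent on masking. A reader might infer that the models were read by someone who knew the arm, but nothing says so, and one sentence from the investigators could settle it. That stands: the point is that no masking is described.

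The size is also open. No document gives a reading bias, a decline curve or the spread of leveling times. The larger rates need exponential decline, a narrow spread of rates and a constant bias in one arm only. Linear decline almost removes the inflation, and a 0.1 mm bias matters little under any shape tested. That stands too, so both curves must be shown.

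Four further inferences are tempting and unsupported:

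- That the periodontal examiner is the only safeguard. The SAP names an intraclass correlation for the Little index itself, though it cannot detect bias by arm.
- That leveling time is the main outcome. The protocol lists five groups of variables and names none as primary.
- That the digital readings alone decide completion. The index is measured on the scans, but the model series ends at a chairside step, and the protocol does not say whether completion was called then or from the scans.
- That the harm is permanent, or that coding cures everything for nothing. Stored scans can be re-read, coding takes some hours, and chairside decisions stay unmasked.

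None of this removes the gap. Followed as written, the procedure leaves open a route for bias that coding would close.

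**Conclusion.** The concern holds as an avoidable weakness in the measurement procedure, not as evidence that readings were biased. Arm is evident from the procedure, leveling time depends on a measured index crossing 1 mm, and no step hides arm or session from the reader.

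The size is conditional. For a bias of 0.1 to 0.3 mm and 4 to 6 months to reach 1 mm, the range runs from a shift of about 1 day with a false-positive rate near 5% (linear) to about 21 days and 26% (exponential, narrow spread of rates). A material effect needs roughly 0.2 mm or more together with slow decline near the threshold. The case for acting rests on the small cost of the remedy, not on the upper end of that range. A cheap improvement that should be made; confidence is medium.

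**What to change.** In Evaluation of Digital Model, state who measures the models, and that:

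- each scan is given a random code with arm, patient and session removed;
- scans are measured in random order by existing staff;
- the code is held by someone who does no reading, and is broken only after the Little index values are locked.

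In Evaluation of Leveling Times and the SAP, derive leveling time for the between-arm test from the masked values. If the models were already read unmasked, re-measure the stored scans under codes and use those values.

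Fix in advance how to handle a patient whose last available model reads 1 mm or more when masked, for example as censored at that visit. The t test in the SAP cannot use censored times, so that choice would also need a time-to-event method such as a log-rank test. State whether completion was called chairside or from the digital readings. If masking was already in place, a sentence describing it replaces the coding text.

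Cost: some hours to code and possibly re-measure files, and one person to hold the code. The sample size stays at 28, with no added visit or procedure. This removes reading bias only. Wire changes and the end of the model series remain decisions made with knowledge of arm, and the report should say so.
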